10.8 Appropriateness of Measurements

The efficacy and safety assessments planned for this study are widely used and generally recognized as reliable, accurate, and relevant to the assessment of biological products administered to patients with CF.

11 STATISTICAL METHODS

11.1 General Considerations

The statistical methods will be further detailed in the Statistical Analysis Plan (SAP).

Any change to the data analysis methods described in the protocol will require an amendment only if it changes a principal feature of the protocol. Any other change to the data analysis methods described in the protocol, and the description for making the change, will be described in the SAP and in the clinical study report. Additional exploratory analyses of the data will be conducted as deemed appropriate.

Statistical methodology and analyses will be in accordance with the principles outlined by the International Council for Harmonisation (ICH) E9 guidelines.

Tables, listings, and figures will be produced in accordance with the principles outlined by the ICH E3 guidelines.

Summaries will consist of descriptive statistics including the nonmissing counts, mean, standard deviation, median, Interquartiles (IQ), minimum and maximum values for continuous variables, and number and percentage of patients in each defined category for categorical variables.

The primary efficacy endpoint analysis aims to compare the mean CFA after receiving adrulipase vs porcine PERT. With the sample size to be employed, primary efficacy analysis will be descriptive rather than inferential.

As a general rule, missing data will not be replaced.

11.2 Sample Size Determination

Based upon CFA data obtained in previous studies with adrulipase, 12 patients per adrulipase dose should provide sufficient point estimates of CFA in each group. Given the acceptable safety profile obtained in the previous study, a sample of 12 patients should be adequate for observation of safety per dose of adrulipase. This study will use descriptive analyses for both safety and efficacy analyses.

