2 SYNOPSIS

Name of Sponsor/Company: First Wave Biopharma, Inc.	
Name of Investigational Product: Adrulipase (formerly MS1819)	
Protocol Number: FWB-CF-2.03	
Protocol Title: A Phase 2, Open Label, Multicenter, Pilot Study to Assess Safety and Efficacy of an Enteric Microgranule Formulation of Adrulipase in Patients with Exocrine Pancreatic Insufficiency (EPI) due to Cystic Fibrosis (CF)	
Study Name: SPAN: A Phase 2, Open Label, Multicenter, Pilot Study to Assess Safety and Efficacy of an Enteric Microgranule Formulation of Adrulipase in Patients with Exocrine Pancreatic Insufficiency (EPI) due to Cystic Fibrosis (CF)	
Study Site(s): This study will be conducted at approximately 3 sites in the United States	
Number of Patients: Approximately 12	Phase of Development: 2
Objectives To establish safety and efficacy of a new enteric microgranule formulation of adrulipase in patients with EPI due to CF.	

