7 STUDY OBJECTIVES

7.1 Primary Objectives

The Primary objective of this pilot study is to establish safety and efficacy of a new enteric microgranule formulation of adrulipase in patients with EPI due to CF.

The primary safety objective of this study is to assess the safety and tolerability of the highest dose received of adrulipase (for subjects under Part 1, 1.2 g/day, 1.95 g/day or 2.4 g/day; for subjects under Part 2, 3.3 g/day) provided in size 00 capsules containing ~150 mg adrulipase. Efficacy will be evaluated by comparing CFA values during treatment with the highest dose of adrulipase versus baseline CFA obtained during screening of the patient's pre-study porcine PERT.

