8 INVESTIGATIONAL PLAN

8.1 Overall Study Design and Plan: Description

This is a Phase 2, single arm pilot study assessing the safety and efficacy of adrulipase in an enteric microgranule formulation. Patients with a confirmed diagnosis of cystic fibrosis who are 18 years of age or greater will be screened for eligibility if they have been clinically controlled, including minimal signs and symptoms of EPI, on a stable dose of commercial pancreatic enzyme replacement therapy (PERT) for at least one month.

Patients on cystic fibrosis transmembrane conductance regulator (CFTR) modulator therapies must have been on a stable dose for at least 3 months prior to study entry, and no dose changes will be made during the study. Patients receiving gastric acid suppressants must have been on a stable dose for at least one month prior to study entry and no dose changes will be made during the study.

Upon obtaining an informed consent, potentially eligible patients will receive dietary counseling during the week prior to confinement for collecting stool samples for calculation of baseline coefficient of fat absorption (CFA). This counseling will emphasize the importance of dietary stability during the study. Patients found to have a CFA of 80% or greater while receiving their commercial PERT and meeting the other eligibility criteria will be enrolled into the study.

The study will enroll patients into either Part 1 (under protocol version 1.0) or Part 2 (under protocol version 2.0). Upon study enrollment, the patient will be switched from their commercial PERT to receive adrulipase. The patient will remain on study for approximately three weeks for Part 1 patients or two weeks for Part 2 patients, after which a repeat CFA will be obtained under supervised confinement. In special circumstances, upon discussion with First Wave BioPharma, the end of study supervised confinement may be done prior to the two or three weeks on adrulipase.

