8.3 Discussion of Study Design

8.3.1 Number of Planned Patients

Approximately 12 patients are planned to complete the study.

The statistical considerations on which the planned number of patients is based are described in [Section 11](#).

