11.5.2 Demographic and Other Baseline Characteristics

Demographic and other baseline characteristics will be summarized in the Safety Set:

- For each dose (i.e., 1.2 g/day, 1.95 g/day, 2.4 g/day, or 3.3 g/day)
- for all patients

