11.7 Efficacy Analysis

11.7.1 Primary Efficacy Endpoint

The primary efficacy endpoint is defined as the CFA assessed at the end of the approximately 21-day treatment period (Part 1) or 14-day treatment period (Part 2). CFA will be calculated as follows:

$$\text{CFA (\%)} = 100 \left(\frac{(\text{fat intake (g)} - \text{fat excretion (g)})}{\text{fat intake (g)}} \right)$$

Primary Analysis:

The primary analysis of the primary endpoint will be a comparison of the mean CFAs from the adrilipase treatment vs the PERT treatment (screening), using descriptive statistics. Data will be analyzed according to the protocol version under which patients enroll (ie, Part 1 [protocol version 1.0] or Part 2[protocol version 2.0]) according to the SAP.

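### Protocol 11.2 bases the sample size on 12 patients per adrulipase dose, but about 12 patients in total cannot give 12 per dose across four doses and two Parts

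*Protocol*

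**What the plan says.** **Section 11.2** makes two per-dose statements. For efficacy, "12 patients per adrulipase dose should provide sufficient point estimates of CFA in each group". For safety, it calls a sample of 12 adequate at each dose.

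**The planned number is a study total.** The synopsis gives "Number of Patients: Approximately 12". Section 8.3.1 says "Approximately 12 patients are planned to complete the study" and continues: "The statistical considerations on which the planned number of patients is based are described in" Section 11.

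**There are four doses in two Parts.** Section 11.5.2 summarises baseline "For each dose (i.e., 1.2 g/day, 1.95 g/day, 2.4 g/day, or 3.3 g/day"). Section 8.1 says "The study will enroll patients into either Part 1 (under protocol version 1.0) or Part 2 (under protocol version 2.0"). Section 8.4.2 assigns every Part 2 patient to 3.3 g/day. Section 7.1 frames the objectives by highest dose received, including "for subjects under Part 2, 3.3 g/day". On the primary endpoint, Section 11.7.1 says: "Data will be analyzed according to the protocol version under which patients enroll".

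**A second rationale appears elsewhere.** The Statistical Methods part of the synopsis and SAP 3.4 justify 12 patients under dose titration and make no per-dose claim. The Study Design part of the synopsis says that Part 2 has no dose optimization.

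**The concern.** The section cited as the basis for the planned number supports a different number. Read literally, 11.2 tells the reader that each dose has enough patients for a CFA point estimate and for a look at safety. The planned total cannot provide that for four doses.

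This matters because results by dose and by Part are planned outputs. Baseline is summarised by dose (11.5.2), CFA is analysed by protocol version (11.7.1), and SAP 9.2 presents the primary endpoint by dose. The gap is most important at 3.3 g/day. Section 6.7 says this dose was not used in prior studies, and it forms a Part of its own. A reader relying on 11.2 would credit that dose with more support than the stated total gives it.

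**Working it through.** **Inputs**

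| Quantity | Value | Source |
|---|---|---|
| Planned total | about 12 | Synopsis; Protocol 8.3.1 (completers) |
| Stated basis | 12 per dose | Protocol 11.2 |
| Doses | 4 (three in Part 1, one in Part 2) | Protocol 11.5.2, 8.4.1 |
| Parts per patient | 1 | Protocol 8.1 |
| In Part 1 when version 2.0 was written | 6, of whom 5 had been dosed at 2.4 g/day | Protocol 6.7 |

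The plan gives no alpha, power, SD or target precision, so there is no sample-size formula to rerun. The check is whether 12 per dose leads to the planned total.

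**Step 1. Reproducing the planned figure.** Total = 12 × number of groups:

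- one group: 12 × 1 = 12, which matches;
- two groups, one per Part: 12 × 2 = 24;
- the three Part 1 doses alone: 12 × 3 = 36;
- four doses: 12 × 4 = 48.

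The planned 12 follows only if there is a single dose group.

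**Step 2. Minimum totals under each way of counting.**

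- *Every dose received counts.* Twelve Part 1 patients who all pass through 1.2, 1.95 and 2.4 g/day, plus twelve Part 2 patients: 12 + 12 = 24. This works for safety exposure. It does not work for CFA by dose, because CFA on adrulipase is measured once, at Visit 6 (Protocol Section 3; SAP 9.2.1), so each patient gives one value at one dose.
- *Highest dose received counts* (Protocol 7.1; SAP 4): 12 × 4 = 48. This is a floor, because Part 1 escalation follows symptoms and would not fill the groups evenly.
- *Only 3.3 g/day must reach 12,* added to the six patients already in Part 1: 6 + 12 = 18.

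**Step 3. What a total of 12 leaves for 3.3 g/day.** 12 − 6 = 6. This is an inference: 6.7 is a snapshot of enrolled patients, 8.3.1 counts completers, and no Part 2 target is given. A range of 5 to 8 is shown below.

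**Step 4. What the smaller group means.** The one-sided 95% upper bound on an event rate after zero events is 1 − 0.05^(1/n). The chance of seeing at least one case of an AE with a true rate of 10% is 1 − 0.9^n. The 10% is an illustration and does not come from the documents.

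| n | Upper bound after zero events | Chance of at least one case at 10% |
|---|---|---|
| 5 | 45% | 41% |
| 6 | 39% | 47% |
| 8 | 31% | 57% |
| 12 | 22% | 72% |

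For mean CFA, the 95% CI half-width in SD units is t(0.975, n−1)/√n. It is 0.635 at n = 12, 1.05 at n = 6 and 1.24 at n = 5. The documents give no SD for CFA. For an assumed SD of 10 to 25 percentage points, the half-width is 6.4 to 15.9 points at n = 12 and 10.5 to 26.2 points at n = 6.

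**The case against.** The strongest reply is that nothing operational depends on the sentence. Protocol 11.1 and 11.2 make the analyses descriptive, SAP 9.1.4 plans no efficacy testing, and the actual counts will be shown. That is correct. It limits the consequence to the justification and to how the by-dose summaries are read, but it does not make the sentence true.

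A second reply is that 48 overstates the gap. Section 7.1 states objectives and 11.5.2 governs baseline tables; neither defines sample-size groups. SAP 4, which classifies patients by maximum dose, lists only the three Part 1 doses. Since 11.7.1 analyses CFA by Part, a group could mean a Part. That reading is possible, and it is why 48 is given only for counting by highest dose. It still requires 24, twice the planned total, and it does not fit the words of 11.2, which refer to each dose.

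Third, the figure of about 6 is inferred, the 10% AE rate is illustrative, and the documents set no precision target. All of this stands. The contradiction between 11.2 and the planned total depends on none of it.

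Finally, SAP 3.4 agrees with protocol version 1.0, on which SAP 2 says it was based. Its silence on Part 2 belongs to a wider version mismatch. That is fair, and it adds no weight here beyond showing that the titration rationale does not fill the gap.

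**Conclusion.** The sample-size statement in Protocol 11.2 is wrong as written and should be corrected. It claims adequacy at 12 per dose, and a total of about 12 does not deliver that under any way of counting patients across the four doses. The shortfall is at least a factor of two (24 against 12) under the most generous count, and at least a factor of four (48 against 12) by highest dose received. If the total stays at 12 and Part 1 stays at the six patients reported in 6.7, 3.3 g/day gets about half the number that 11.2 calls adequate. The titration rationale in the synopsis and SAP 3.4 cannot replace 11.2 for Part 2. No type I error, power or endpoint definition is affected.

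**What to change.** Reconcile 11.2 with the synopsis and 8.3.1. If about 12 in total is intended, the two per-dose sentences could be replaced by text such as:

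> About 12 patients in total are planned: about [n] in Part 1 and about [n] in Part 2, with about [n] expected at each highest dose received. No per-dose sufficiency is claimed for CFA or safety.

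The sponsor has to supply the numbers and say whether they count enrolled patients or completers. The last sentence of the suggested text is optional, provided the per-dose wording is removed and the numbers per Part are stated.

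If 12 per dose is intended, put the matching total in the synopsis and 8.3.1, and say how a titrated patient is counted.

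In either case, revise the rationale in the synopsis and SAP 3.4 so that it covers Part 2.

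If the total stays at about 12, the cost is wording only: no endpoint, analysis set or patient procedure changes. The sample-size statement becomes less favourable. Keeping the per-dose claim would mean enrolling more patients.

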11.3 Analysis Sets

- Safety Set: patients receiving at least one dose of treatment. Patients will be analyzed according to the treatment actually received. The Safety Set will be used for all analyses of safety endpoints unless specified otherwise and for the summaries of patients in listings related to dosing of study drug.
- Efficacy sets:
 - mITT Set: All randomized patients receiving at least one dose of treatment and have at least one valid stool collection and CFA post baseline while receiving their assigned study drug. The mITT set is considered as the primary set for the efficacy analysis. The mITT set will be used for all analyses of efficacy endpoints.
 - Per Protocol Set: Subset of the mITT set comprising all patients who do not violate the terms of the protocol in a way that would affect the study outcome significantly, as determined by the study clinician. Protocol

deviations will be captured throughout the study and classified as minor or major and reviewed at a data review meeting before database lock. Attendees will include appropriate individuals from First Wave BioPharma and contract research organization. Each major deviation will be categorized as either important or not important with respect to the effect on the primary endpoint analysis. A sensitivity analysis will be performed in the Per Protocol Set.

11.4 Handling Missing Data

Missing data will not be replaced.

11.5 Demographic, Other Baseline Characteristics and Medication

Demographics, other baseline characteristics, and medications will be summarized for the Safety Set unless specified otherwise.

11.5.1 Patient Disposition and Withdrawals

The following will be summarized:

- Number of screen failures
- Number of patients included in the ITT, and PP sets
- Number of patients who completed the study
- Number of patients who discontinued the study early with reasons

The patient disposition, and protocol deviations will be listed.

11.5.2 Demographic and Other Baseline Characteristics

Demographic and other baseline characteristics will be summarized in the Safety Set:

- For each dose (i.e., 1.2 g/day, 1.95 g/day, 2.4 g/day, or 3.3 g/day)
- for all patients

11.6 Safety Analysis

Safety (AEs, SAEs, discontinuations due to adverse events, and safety laboratory values) will be assessed by descriptive methods.

11.7 Efficacy Analysis

11.7.1 Primary Efficacy Endpoint

The primary efficacy endpoint is defined as the CFA assessed at the end of the approximately 21-day treatment period (Part 1) or 14-day treatment period (Part 2). CFA will be calculated as follows:

$$\text{CFA (\%)} = 100 \left(\frac{(\text{fat intake (g)} - \text{fat excretion (g)})}{\text{fat intake (g)}} \right)$$

Primary Analysis:

The primary analysis of the primary endpoint will be a comparison of the mean CFAs from the adrilipase treatment vs the PERT treatment (screening), using descriptive statistics. Data will be analyzed according to the protocol version under which patients enroll (ie, Part 1 [protocol version 1.0] or Part 2[protocol version 2.0]) according to the SAP.

11.7.2 Secondary Efficacy Endpoints

Coefficient of nitrogen absorption (CNA) will be calculated and analyzed in the same manner as CFA.

Stool weights, signs and symptoms for malabsorption, body weight, and will be analyzed using descriptive methods.

12 QUALITY ASSURANCE AND QUALITY CONTROL

12.1 Audit and Inspection

An audit/inspection may be carried out by qualified First Wave BioPharma staff member, by subcontracted auditors or by representatives of national or foreign Health Authorities to ensure that the study is conducted as per protocol and in accordance with regulatory requirements, and to ensure the validity of the data. Participation in this study implies acceptance to cooperate in any potential audit/inspection.

The audit/inspection may consist of an inspection of the premises and equipment together with verification of the study documents and data. The investigational team must be available for inspection or audit. When First Wave BioPharma or the Investigator is informed that an inspection is to be performed, the other party must be informed immediately.

Audits/inspection may take place after the end of the study.

12.2 Monitoring

Data for each patient will be recorded on a CRF by the investigational site. Data collection must be completed for each patient who signs an informed consent form (ICF).

In accordance with cGCP and ICH guidelines, the study monitor will carry out source document verification at regular intervals to ensure that the data collected in the CRF are accurate and reliable.

The Investigator must permit the monitor, the IEC/IRB, the First Wave BioPharma's internal auditors, and representatives from regulatory authorities, direct access to all study-related documents and pertinent hospital or medical records for confirmation of data contained within the CRFs.

12.2.1 Responsibilities of the Monitor

Instructions for monitoring will be documented in a clinical monitoring plan. The clinical monitoring plan will include options for off-site/remote data verification.

The responsibilities of the study monitor are defined in ICH-E6, Chapter 5. The Monitor, who is mandated by First Wave BioPharma, must ensure that the study is conducted in accordance with GCP guidelines and all applicable local laws, and that the rights, the security and the well-being of the patients are respected.

During the conduct of the study, the monitor reports any deviations or persistent poor compliance with the study requirements and First Wave BioPharma will make decisions about appropriate corrective actions.

Compliance:

- The monitor has the responsibility of assessing the progress of the study, checking that the informed consent forms have been signed by the patient ensuring adhesion to and compliance with the study protocol and other study-related documents, and of ensuring the accuracy and completeness of the CRFs. Inconsistencies in the study records are to be resolved.

Source Data Verification:

- The monitor will perform source document verification and validation and request clarification to ensure the accuracy, completeness, and reliability of data.

Investigational Medicinal Product:

- The monitor must ensure that IMP handling is properly carried out and documented.

He/she must ensure that the Investigator site file is up to date with regard to essential documents.

12.3 Data Management and Coding

The assigned contract research organization will be responsible for activities associated with the data management of this study. This will include setting up a relevant database and data transfer mechanisms, along with appropriate validation of data and resolution of queries.

Investigational sites will enter data directly into an electronic data capture system by completing the CRF. Data entered into the eCRF must be verifiable against source documents at the study center. Data to be recorded directly on the eCRF will be identified and the eCRF will be considered the source document. Any changes to the data entered into the electronic data capture system will be recorded in the audit trail and will be FDA CFR 21 Part 11 compliant.

13 ETHICS

13.1 Ethics and Regulatory Considerations

The current study is to be conducted in accordance with globally accepted standards of GCP (ICH-E6), the Clinical Trial Directive 2001/20/EC, the GCP Directive 2005/28/EC, the revised version of the Declaration of Helsinki set out in the European Directive, and with applicable local requirements.

The protocol will be submitted to the Health Authorities and a properly constituted IEC or IRB for formal approval of the study conduct in accordance with local regulations.

The study may not begin until the protocol has received appropriate approval from the Health Authorities in accordance with local requirements.

In accordance with specific local requirements, the Investigator may be responsible for submitting the protocol and any amendments to the local IEC/IRB. A copy of the decision letter, a list and versions of documents submitted, and a list of IEC/IRB members and their affiliation should be provided by the Investigator to First Wave BioPharma.

During the study, First Wave BioPharma should promptly notify the Investigators and Health Authorities of any relevant information that could affect the safety of patients or effect on the conduct of the study. The regulatory authorities will be notified that the study has ended on completion of the study.

13.2 Ethical Conduct of the Study

The Investigator(s) and all parties involved in this study should conduct the study in adherence to the ethical principles based on the Declaration of Helsinki, GCP, ICH guidelines, and applicable national laws, local laws, and regulatory requirements.

13.3 Informed Consent

An IRB/IEC approved telephone informed consent to ensure that subjects come into clinic only if interested in proceeding with screening procedures is encouraged.

Before a patient's participation in this clinical study, the Investigator is responsible for obtaining written informed consent from the patient or legally acceptable representative after adequate explanation of the aims, methods, anticipated benefits, and potential hazards of the study and before any protocol-specific screening procedures or any investigational products

are administered. A legally acceptable representative is an individual or other body authorized under applicable law to consent, on behalf of a prospective patient, to the patient's participation in the clinical study. The Investigator is also responsible for asking the patient if the patient agrees to have his/her primary care physician informed of the patient's participation in the clinical study. If the patient agrees to such notification, the Investigator shall inform the patient's primary care physician of the patient's participation in the clinical study.

The acquisition of informed consent and the patient's agreement or refusal of his/her notification of the primary care physician should be documented in the patient's medical records, and the informed consent form should be signed and personally dated by the patient or a legally acceptable representative and by the person who conducted the informed consent discussion (not necessarily an Investigator). The original signed informed consent form should be retained in accordance with institutional policy, and a copy of the signed consent form should be provided to the patient or legally acceptable representative.

If a potential patient is illiterate or visually impaired and does not have a legally acceptable representative, then the Investigator must provide an impartial witness to read the informed consent form to the patient and must allow for questions. Thereafter, both the patient and the witness must sign the informed consent form to attest that informed consent was freely given and understood.

